In addition to evaluating the primary outcome of BP and LDL control at year 3, these parameters will also be evaluated year 1 after randomization. For lipid parameters, in addition to the LDL-C goal attainment, NonHDL goal attainment (<130/ mg/dL) and the LDL/HDL ratio <2.0) will be evaluated at years 1 and year 3. No additional contacts will be made to obtain these readings outside of the intervention/usual care practices. Values available in the medical record \pm 180 days of year 1 will be used for assessing this outcome. If no values are available in this timeframe, just the available data will be analyzed and compared.

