3.2. Evidence-Based Medications

3.2.a. Antiplatelet/Antithrombotic Medications: Prescriptions for antiplatelet therapy (dipyridamole/aspirin, ticlopidine, clopidogrel and/or prasugrel) or anticoagulation therapy (warfarin) will be assessed at 1 and 3 years after randomization for both groups. Patients will be considered persistent to these medications if days supply/sold date (\pm 15 days) overlaps the date of the 1 and 3 year timeframes. Aspirin use will only be collected by patient report at baseline and at 3 years for both groups. This is an over-the-counter medication that is not tracked in the KPCO prescription databases. The only way to capture ASA data will be through patient report.

3.2.b Antihyperlipidemic Medications: In addition to lipid goal attainment, the prescription antihyperlipidemic medications and dose the patient is taking will be collected at 1 and 3 years for both groups. The medications will be classified as statin, fibric acid derivatives, ezetimibe, nicotinic acid (i.e. Niaspan®), bile acid sequestrants, or other. Patients will be considered persistent to the lipid-lowering therapy if the days supply overlaps the date (\pm 15 days) of their FLP result at each time point.

3.2.c. Antihypertensive Medications: In addition to blood pressure goal attainment, the antihypertensive medications and dose the patient is taking will be collected at each time point (1 and 3 years). Medications will be classified into therapeutic classes (i.e. thiazide diuretic, ACE inhibitor, β -blocker, calcium channel blocker, etc). Patients will be considered to be persistent to antihypertensive therapy if the days supply (\pm 15 days) overlaps the date of their blood pressure assessment.

3.3. Smoking Cessation: Smoking cessation will be assessed for both groups at baseline and study end (year 3) per patient report and will be coded as current, past (quit 5 years ago), or never. Smoking will include any nicotine products (cigarettes, cigars, pipes) and chewing tobacco. The quantity smoked or second-hand smoke exposure will not be captured.

Sample Size Calculation

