For the primary outcome of proportion at both BP and LDL-c goals at year 3, and based on prior studies,²⁸ we estimate that 45% of patients in the Usual Care group will meet the end point at 3-years and conservatively estimate that 60% the CPCRS intervention will meet the end point. An enrollment number of 173 patients per group will be required, with a two-sided alpha of 0.05 and power of 80%. To account for about a 20% dropout rate, the number will be inflated to 200 patients per group.

It is estimated that approximately 5200 patients will have validated stroke, of which

4200 will have ischemic stroke (both cardioembolic and non-cardioembolic and approximately 2500 will have non-cardioembolic ischemic stroke. We anticipate that with this pool of patients, we should be able to meet this sample size calculation.

Statistical Analysis

All statistical analyses will be performed on an intention-to-treat basis utilizing SAS (SAS, Cary, NC) statistical software. Baseline subject characteristics for each study group will be reported as means, medians, and standard deviations for interval- and ratio-level variables (e.g., age, length of time between events, mean lipid levels) and percentages for nominal- and ordinal-level data (e.g., sex, cardiovascular event history). All patients who completed follow-up in their randomized intervention assignment at years 1 and years 3 (as outlined in outcomes assessment) will be included regardless of whether they interacted with CPCRS or not. Interval-level outcome variables will be assessed for normality of their distributions and appropriate tests (e.g., t-test, rank-sum test) will be used to assess differences in mean values between groups. Study outcomes will be dichotomized as yes/no (e.g., reached BP & LDL goal levels yes/no, persistent

with lipid-lowering therapy yes/no). To assess differences in proportions between groups on dichotomous outcome variables, Pearson's chi-square test of association will be utilized. An alpha < 0.05 will be considered statistically significant.

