Follow-up for Laboratories and Blood Pressure Values: The HealthTrac-Stroke® disease registry will be used to schedule follow-up contacts in order to minimize the number of subjects lost to follow-up. Letters will be mailed to subjects in the Intervention group reminding him/her to have appropriate laboratories completed, as necessary, using standard CPCRS letters. Patients who fail to have laboratories drawn after 2 mailed reminder letters separated by 1-month will be marked "noncompliant" in the database and receive reminders every 6 months thereafter.

For patients in the Usual Care group, no reminder letters will be sent. However for assessment of lipid and blood pressure control at 3 years (primary outcome)

for both groups, reminder letters will be mailed, if necessary (Appendix VI).

Study end: All patients will be followed for 3 years from randomization or until the first occurrence of KPCO termination date, cardiovascular event, or death.

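### The analysis labelled intention-to-treat is restricted to patients who completed follow-up, and the year-1 and drug-persistence comparisons depend on testing that differs by arm

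*Protocol*

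**What the plan says.** Protocol section 33.1, Statistical Analysis, states the principle: "All statistical analyses will be performed on an intention-to-treat basis". Later in the same paragraph it defines who is analysed: "All patients who completed follow-up in their randomized intervention assignment at years 1 and years 3 (as outlined in outcomes assessment) will be included". That sentence goes on to say that inclusion does not depend on whether the patient had any contact with the pharmacist service (CPCRS).

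Other parts of the protocol bear on who completes and who has a value:

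- **End of follow-up (section 45, Study end).** Follow-up lasts 3 years, or until the first of health-plan termination, a cardiovascular event or death.
- **Year 3 (section 33.1, Primary Outcome Measure).** Both arms get the same two letters, then a call. A non-fasting lipid panel is accepted as a fallback, and free blood pressure (BP) visits are offered.
- **Year 1 (section 33.1, Tertiary Outcomes 3.1).** No contact is made beyond what each arm's care provides, and values within 180 days either side are used. "If no values are available in this timeframe, just the available data will be analyzed and compared".
- **Reminders during follow-up (section 45).** The intervention arm gets laboratory reminder letters and yearly laboratory and BP checks. "For patients in the Usual Care group, no reminder letters will be sent", except those for the 3-year assessment.
- **Drug persistence (section 33.1, Tertiary Outcomes 3.2).** For lipid-lowering drugs: "Patients will be considered persistent to the lipid-lowering therapy if the days supply overlaps the date" of the lipid result. Antihypertensive persistence is tied in the same way to the date of the BP assessment. Antiplatelet and anticoagulant persistence instead asks whether supply "overlaps the date of the 1 and 3 year timeframes".

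**The concern.** Intention-to-treat and completers only are different analysis sets, and the protocol prescribes both. Followed as written, the report would carry the first name and the second content.

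Completion is decided after randomisation. Because follow-up stops at a cardiovascular event or death, and hypothesis 1b predicts fewer of these in the intervention arm, the trial's own hypothesis says that completion may differ by arm. Randomisation then no longer protects the comparison of those who remain, including for the primary outcome.

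For two groups of tertiary outcomes, having a value also depends on a testing schedule that differs by arm. At year 1 each arm is judged on whatever values its own care produced. For lipid-lowering and antihypertensive persistence, a patient with no lipid or BP result has no date at which to be classified. This bears on hypothesis 1c.

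**Working it through.** **1. Does the sample size treat dropouts as lost?** The inputs are in section 33.1. For usual care: "we estimate that 45% of patients in the Usual Care group will meet the end point at 3-years". The rate assumed under the intervention is 60%, with two-sided alpha 0.05 and 80% power. With pooled variance under the null,

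n = [1.960·√(2·0.525·0.475) + 0.842·√(0.45·0.55 + 0.60·0.40)]² / 0.15² = (1.384 + 0.588)² / 0.0225 ≈ 172.8, so 173 per group.

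This reproduces the plan's figure. The plan then enrols 200 per group to allow for about 20% dropout, so dropouts are expected to leave the analysis. At 20% loss, 200 × 0.80 = 160 remain per group, with power 76.9%.

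**2. Which patients does the rule remove?** Someone who never spoke to a pharmacist but has year-3 values is kept. Someone who died, left the plan or has no values is not a completer of 3-year follow-up. The protocol does not say whether a patient whose follow-up ended at a cardiovascular event counts as having completed it. Read literally, with the outcome set at 3 years, that patient does not.

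**3. What could the exclusion do?** Let m be the fraction unmeasured in an arm and q the proportion at goal among the unmeasured. If 45% of the whole arm is truly at goal, completers show

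(0.45 − m·q) / (1 − m).

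The protocol gives neither m by arm nor q, so both are assumptions. The true difference is zero in every row; differences are intervention minus usual care.

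| m, intervention / usual care | q, intervention / usual care | Completers show | Spurious difference |
|---|---|---|---|
| 20% / 20% | 25% / 25% | 50.0% / 50.0% | 0 |
| 10% / 20% | 30% / 30% | 46.7% / 48.8% | -2.1 points |
| 10% / 25% | 25% / 25% | 47.2% / 51.7% | -4.4 points |
| 10% / 30% | 25% / 25% | 47.2% / 53.6% | -6.3 points |
| 20% / 20% | 25% / 60% | 50.0% / 41.3% | +8.8 points |

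Third row in full: (0.45 − 0.10·0.25)/0.90 = 0.472 and (0.45 − 0.25·0.25)/0.75 = 0.517. The difference of -4.4 points is 4.4/15, about 30% of the planned effect. With 200 randomised per arm, a nominal 5% test would reject in 20.3% of trials in the fourth row and 34.8% in the fifth.

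**4. How far do completers pin down the full comparison?** Suppose completers show exactly 60% vs 45%, with 20% unmeasured in each arm. The known at-goal fractions of all randomised are 0.60·0.80 = 0.48 and 0.45·0.80 = 0.36. The extremes are 0.48 − (0.36 + 0.20) = -8 points and (0.48 + 0.20) − 0.36 = +32 points.

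**5. Persistence.** The protocol does not say how a patient without a lipid or BP result is coded. If excluded, the comparison is among tested patients only. If coded as not persistent, the arm tested less often looks worse. Either way the testing schedule enters a drug outcome that pharmacy records can supply without it, as the antiplatelet definition shows.

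**The case against.** The strongest reply is that the primary outcome is well protected. A reader who sees that usual care gets no reminders might infer that year-3 ascertainment is unequal by design. The documents do not support that: the next sentence of the same section provides 3-year reminders for both groups, and section 33.1 gives both the same letters, calls and BP visits. Yearly checks in the intervention arm might leave some imbalance at year 3, but nothing in the protocol shows how much.

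A reader might also take this for a per-protocol analysis. It is not, because contact with the service is expressly irrelevant to inclusion. That is a genuine intention-to-treat element, but it does not bring back patients without an outcome.

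On the tertiary outcomes, the year-1 window is wide, the reminder letters concern laboratories rather than BP, and tying persistence to the test date has a rationale: it shows whether the value was measured on treatment. The drugs themselves are also collected at 1 and 3 years. These points lower the weight of the tertiary part without removing it. Dispensing data also do not cover everyone, since they stop when a patient leaves the plan.

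Finally, the method for missing data may properly sit in a statistical analysis plan that is not shown. The analysis set, however, is fixed in the protocol, and a later plan that follows it would inherit the conflict.

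**Conclusion.** The contradiction stands and should be corrected before analysis. The protocol names intention-to-treat and prescribes completers as randomised, with about 20% loss expected and follow-up ending at events that hypothesis 1b expects to differ by arm. For the primary outcome the fault is the exclusion of non-completers, not arm-specific reminders. Built-in unequal ascertainment is confined to the year-1 available-data comparison and to lipid-lowering and antihypertensive persistence. These are tertiary and less serious.

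A reader might infer that the plan yields a bias of known size, or one that favours the intervention. It does not. The differences of -2.1, -4.4, -6.3 and +8.8 points rest on assumed missingness and assumed goal rates among the unmeasured, and applying 45% to year 1 would be a further assumption. With equal loss and the same goal rate among the lost, the bias is zero. The protocol determines neither size nor direction.

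**What to change.** Replace the completer sentence with: *All randomised patients are analysed in their assigned arm.* Then state the following.

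- **Missing year-3 BP or LDL-C in living patients:** multiple imputation by arm from baseline and interim chart values, with missing-as-not-at-goal and tipping-point sensitivity analyses.
- **Death:** a separate explicit rule, for example counted as not at goal. BP and LDL-C should not be imputed for patients who have died.
- **Cardiovascular event, still a member:** use any chart values within the year-3 window.
- **Plan exit:** treat as missing.
- **Year 1:** the same approach in place of the available-data comparison.
- **Persistence with lipid-lowering and antihypertensive drugs:** assess on the fixed 1- and 3-year dates from dispensing data for all current members, tested or not, as is already done for antiplatelet drugs.

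The cost is revised wording and modest extra programming on data already held. The downside is a possibly smaller observed difference when missing counts as not at goal. With 20% unmeasured in each arm, the planned 60% vs 45% becomes 48% vs 36%, a difference of 12 points, and power with 200 per group is 68.3%. For comparison, power is 85.4% with complete data on 200 per group.

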31.0 Hypothesis and Objectives

31.1 Explain the hypothesis and objectives for this study. - For help with this section of the form please click on the help button.

Aim 1: Conduct a randomized, controlled, study of a clinical pharmacist-led disease management intervention for patients with a history of non-cardioembolic ischemic stroke compared to usual care.

Hypothesis 1a: More patients in the clinical pharmacy specialist-led disease management group will achieve their lipid and blood pressure goals compared to the "Usual Care" group.

Hypothesis 1b: Fewer patients randomized to the clinical pharmacy specialist-led disease management group will have recurrent cardiovascular events or death compared to patients in the "usual care" group.

Hypothesis 1c: More patients with ischemic stroke will receive appropriate secondary prevention care using evidence-based medications in the intervention group compared to usual care.

Significance: To our knowledge, this will be the first, prospective, randomized study to evaluate the impact of a clinical pharmacist disease management program on both surrogate and clinical outcomes for patients with non-cardioembolic ischemic stroke.

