Follow-up for Laboratories and Blood Pressure Values: The HealthTrac-Stroke® disease registry will be used to schedule follow-up contacts in order to minimize the number of subjects lost to follow-up. Letters will be mailed to subjects in the Intervention group reminding him/her to have appropriate laboratories completed, as necessary, using standard CPCRS letters. Patients who fail to have laboratories drawn after 2 mailed reminder letters separated by 1-month will be marked "noncompliant" in the database and receive reminders every 6 months thereafter.

For patients in the Usual Care group, no reminder letters will be sent. However for assessment of lipid and blood pressure control at 3 years (primary outcome) for both groups, reminder letters will be mailed, if necessary (Appendix VI).

Study end: All patients will be followed for 3 years from randomization or until the first occurrence of KPCO termination date, cardiovascular event, or death.

45.2 **Explain the Participant Identification and Recruitment Procedures. For assistance with this question please click on the HELP BUTTON.**

Patient Screening for Eligibility: All patients with ICD-9 codes 430.XX to 438.XX (estimated to be approximately 15,000 patients at KPCO) will be administratively identified from KPCO claims databases starting January 1, 2000 and administratively pulled into a HealthTrac®-Stroke registry. Each patient included in the registry will undergo a validation process to ensure stroke type and event dates are accurate (Appendix I). This validation process will be similar to that used for the HealthTrac®-CAD registry already used by CPCRS.

Staff at CPCRS will manually review the electronic medical record for each patient in the registry to ensure the ICD-9 code for stroke is accurate according to detailed procedures (Appendix I). Patients with history that indicates

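### The general yes/no chi-square rule makes no exception for cardiovascular events and death, although follow-up for them is unequal by design

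*Protocol*

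**What the plan says.** Hypothesis 1b (section 31.1) is that "Fewer patients randomized to the clinical pharmacy specialist-led disease management group will have recurrent cardiovascular events or death" than under usual care. Section 33.1, items 2.1.a to 2.1.c, makes cardiovascular events, hospitalizations and death secondary outcomes. Cardiovascular events are to be assessed both as a composite and by component.

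The Statistical Analysis paragraph of section 33.1 gives the method in general terms: "Study outcomes will be dichotomized as yes/no". The bracketed examples are reaching the BP and LDL goals and persistence with therapy. The test follows: "To assess differences in proportions between groups on dichotomous outcome variables, Pearson's chi-square test of association will be utilized". The protocol names no time-to-event, censoring or competing-risk method.

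The same paragraph makes two statements about who is analysed: "All statistical analyses will be performed on an intention-to-treat basis", and "All patients who completed follow-up in their randomized intervention assignment at years 1 and years 3 (as outlined in outcomes assessment) will be included", whether or not they interacted with the pharmacy service.

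The Study end paragraph of section 45.1, repeated under Study Procedures in section 45.3, fixes the observation period: "All patients will be followed for 3 years from randomization or until the first occurrence of KPCO termination date, cardiovascular event, or death".

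**The concern.** A simple proportion is a sound summary of 3-year risk when everyone is observed for 3 years or until the event. Here some patients leave observation at plan termination without an event. Coded no, they count as event-free for time in which nobody was watching. This lowers the estimated risk in both arms, and it distorts the comparison if patients leave at different rates in the two arms.

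Two further difficulties come from the same text. First, if the sentence on completed follow-up is applied to events and death, it can be read as leaving out patients whose follow-up ended early because of the very outcome being counted. That would conflict with the intention-to-treat statement beside it. Second, because follow-up stops at the first cardiovascular event, a later death or a different component event falls outside the defined observation period, although section 33.1 wants death and the components assessed separately.

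At stake is the answer to Hypothesis 1b, not the primary outcome.

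**Working it through.** **The plan's own figure.** The protocol gives no calculation for events or death. Its only sample size figure is for the primary outcome (45% vs 60%, two-sided alpha 0.05, power 80%):

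n = [1.960 × √(2 × 0.525 × 0.475) + 0.842 × √(0.45 × 0.55 + 0.60 × 0.40)]² / 0.15² = 172.8, so 173 per group.

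This matches the protocol and is not in question here.

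**Inputs.** From section 30.1: recurrent stroke 4% per year and death 9.1% per year, used as a low and a high illustrative event rate. From section 33.1: about 20% dropout and 200 patients per group. Assumed: constant hazards, and the disenrolment rates marked as assumed below.

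**Step 1: true 3-year risk.**
- 4% per year: 1 − 0.96³ = 11.5%, about 23 of 200 per arm.
- 9.1% per year: 1 − 0.909³ = 24.9%, about 50 of 200 per arm.

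**Step 2: proportion observed if early leavers are coded no.** With event hazard h and disenrolment hazard c, the observed proportion is h/(h+c) × (1 − exp(−3(h+c))).

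Taking the whole 20% dropout as disenrolment over 3 years, c = −ln(0.80)/3 = 0.0744.
- 4% per year: h = −ln(0.96) = 0.0408. Observed = 0.0408/0.1152 × (1 − 0.96³ × 0.80) = 0.354 × 0.292 = 10.4%, against a true 11.5%.
- 9.1% per year: h = −ln(0.909) = 0.0954. Observed = 0.0954/0.1698 × (1 − 0.909³ × 0.80) = 0.562 × 0.399 = 22.4%, against a true 24.9%.

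**Step 3: effect on the comparison (disenrolment hazards assumed).** Ratios are intervention to Usual Care.

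| Disenrolment hazard per year, Usual Care / intervention | True HR | Crude risk ratio at 4% per year | Crude risk ratio at 9.1% per year |
|---|---|---|---|
| 0 / 0 | 0.84 | 0.848 | 0.859 |
| 0.10 / 0.10 | 0.84 | 0.848 | 0.858 |
| 0.10 / 0.05 | 0.84 | 0.910 | 0.919 |
| 0.10 / 0.05 | 1.00 | 1.073 | 1.071 |
| 0.05 / 0.10 | 1.00 | 0.932 | 0.934 |

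Equal disenrolment hardly moves the ratio. A twofold difference moves it by about 7% in either direction. The HR of 0.84 is the stroke result of the secondary-prevention statin trial described in section 30.1.

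**Step 4: the sentence on completed follow-up.** If it were applied to events and death, and an event did not count as completing follow-up, the patients left out would be those of step 1: about 23 to 50 per arm at these rates.

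**Step 5: power.** With 200 per arm, complete follow-up and an HR of 0.75 (assumed) to 0.84, log-rank power is Φ(|ln HR| × √E / 2 − 1.96), where E is the total number of events.
- 4% per year: E of about 41 to 43, power 8% to 15%.
- 9.1% per year: E of about 88 to 93, power 13% to 27%.

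Chi-square power is within 1 percentage point of these values throughout.

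**The case against.** No sentence says that events and death will be tested by chi-square. The bracketed examples are goal attainment and persistence, and a survival method for secondary outcomes could sit in an analysis plan that is not shown. This stands in part: applying the rule to events is an inference. But the rule is worded for study outcomes in general, its examples are only examples, and nothing exempts events. It is therefore a choice the protocol states, not merely a detail it leaves open.

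Hypothesis 1b asks whether fewer patients have events, which is a question about proportions, and with similar retention chi-square remains an approximately valid test of no difference. This stands. In that case the harm is mainly to the absolute risks, and discarding event times costs almost no power.

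A reader might infer that the completed-follow-up sentence removes every patient who died or had an event, so that no deaths are analysed. The documents do not support this as the plan's meaning. The sentence is tied to years 1 and 3 and to the outcome assessments, time points that section 33.1 gives to the surrogate measures. It does not say that only these patients are included, and it follows an intention-to-treat declaration. Reaching an event can also be read as completing follow-up as section 45.1 defines it. What remains is an ambiguity worth removing.

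A reader might also infer that a false treatment difference is to be expected. With a hazard of 0.13 per year in both arms and assumed disenrolment hazards of 0.05 and 0.10 per year, the formula in step 2 gives 30.1% and 28.2% against a true 32.3%. That gap of about 2 points comes wholly from the assumed split between arms. The hazard adds the stroke and death rates as if they did not overlap, which is an upper bound for those two outcomes together. At 200 per arm, the gap is under half a standard error: √(2 × 0.29 × 0.71 / 200) is about 4.5 points.

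**Conclusion.** The point holds in a limited form. The stated general rule does not suit outcomes whose observation time varies by design, and a better standard method is available. If the expected 20% dropout is all disenrolment, equal in both arms, 3-year risk is understated by about 1 point at 4% per year and about 2.5 points at 9.1% per year, with the ratio between arms nearly unchanged. Bias in the comparison needs disenrolment to differ by arm, and the documents give no basis for saying that it will. That Hypothesis 1b cannot be answered at all would be too strong a conclusion.

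The figures assume constant hazards and background rates that may not fit this selected population. Those rates also leave out coronary and revascularization events. Separately, the study-end rule in sections 45.1 and 45.3 does not fit the separate assessment of death and components in section 33.1. That needs more than a change of analysis wording.

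**What to change.** 1. In section 33.1, limit the yes/no chi-square rule and the sentence on completed follow-up at years 1 and 3 to goal attainment and persistence.
2. Analyse the composite and all-cause death as time from randomization to first event in all randomized patients, censored at KPCO termination or 3 years. Report Kaplan-Meier curves, a log-rank test and a Cox hazard ratio with 95% CI. For non-fatal components, use cumulative incidence with death as a competing event. State the assumption that plan termination is unrelated to event risk, and report termination by arm so that it can be judged.
3. Reconcile the study-end rule in sections 45.1 and 45.3 with items 2.1.a and 2.1.c of section 33.1, so that administrative ascertainment of death and other components continues after a first non-fatal event, to 3 years or termination. This concerns data capture only, not patient care.

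The cost is small. Events and deaths are already captured administratively and the termination date already defines study end, so the extra work is a somewhat longer data capture for patients with a non-fatal event. Little or no power is gained; the benefit is proper handling of censoring and a comparison that includes every randomized patient.
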